#### Opportunistic arm

- 1) Using electronic GP record searches: The proportion of eligible women who:
  - consult their GP practice
  - are offered a self-sampling kit
  - · accept a self-sampling kit
  - return an adequate self-sample.

We will also examine:

- 1) reasons why eligible women are not offered the self-sampling kit
- 2) reasons why eligible women decline self-sampling kits (if offered)

#### Individually randomised women

- 1) The proportion of eligible women in Group B who order a self-sampling kit
- 2) The proportion of eligible women in Group B and Group C who return a self-sample.

#### All women in the study who return a self-sample

- 1) The proportion of women who return an adequate sample
- The proportion of women who test HPV negative who attend for cervical cytology after returning a self-sample
- 3) The proportion of women who test HPV positive, and of these:
  - The proportion of women who attend for cervical cytology
  - The proportion with abnormal cytology
  - The proportion with CIN2+ on histology

#### All women who return a self-sample and all individually randomised women

We will examine the passive follow up data to determine if we can extract:

 Change in cervical screening coverage at each practice (to assess the impact of selfsampling on coverage):

- Cervical screening status at the end of the passive follow up period (aggregate anonymous data and/or individual anonymous data for women who return a selfsample from GP records)
- 3) Cytology and histology (if available) results for women who return a self-sample (if applicable)
  - The proportion with abnormal cytology
  - The proportion with CIN2+ on histology

#### 8.3. End of study definition

The study will end once the following have been completed:

- up to 12 months of active recruitment,
- 6 months follow up (from the date the last HPV positive result on an ALOHA selfsample is reported),
- follow-up data monitoring and
- data collection and cleaning.

Please note: In light of the current COVID-19 pandemic the end of follow up date will depend on when cervical screening services are resumed. i.e. those who tested positive on their ALOHA HPV self-sample will need to be given 6 months at a time when services are available to attend for their follow-up screening.

#### 9. DATA HANDLING AND RECORD KEEPING

Study data will be stored securely and made available for audit according to the standard procedures of King's College London.

#### 9.1. Confidentiality

Information related to participants will be kept confidential and managed in accordance with the Data Protection Act 2018, NHS Caldicott Principles, UK Policy Framework for Health and Social Care Research (2017), and the conditions of Research Ethics Committee Approval.

#### 9.2. Data collection

For study management purposes the study team will require access to patient identifiable data for the following reasons;

- to fulfil kit postal orders to be sent women will have submitted a postal order form
- to send repeat sample kits women will have returned a sample i.e. consented
- to generate HPV results letters women will have returned a sample i.e. consented
- to resolve queries i.e. or to confirm the identity of women for samples returned without a lab request form women will have returned a sample i.e. consented

The study team will also require access to patient identifiable medical record data for monitoring purposes (for those who have returned a sample).

Self-test order forms will be received by the ALOHA study team by post at KCL. The data will be uploaded to PSL print management Ltd web-based SFTP portal and approved third parties (securely via the AIMES Health Cloud). Forms will be stored securely in a locked cabinet in a restricted access office in Guy's Hospital.

Personal data (line-level) will only be downloaded from the GP medical records by the ALOHA trial coordinator for women who return a self-sample i.e. those in the intervention arms who have consented by returning a sample.

Identifiable data will be accessed by the study team on secure web-based reporting platforms using the 'AIMES Health Cloud'. The AIMES Health Cloud is a dedicated virtual environment that enables NHS Trusts to use cloud technologies managing sensitive data in a secure governed environment. The AIMES Health Cloud is only connected to either the Secure NHS Network (N3/HSCN) or directly to individual NHS Trusts with no direct route to the Internet.

At the end of the study personal identifiers will be removed and data will be stored and analysed using the participant's SK number/ unique ID number.

Only anonymous aggregate data or pseudonymised line-level data will be collected for women who are eligible for the study but are 1) in one of the intervention arms but do not return a self-sample or 2) in one of the control groups (at GP level randomisation or individual level randomisation).

We plan to collect:

 Age / sex / ethnicity breakdown of all registered patients – anonymous aggregate data only

- Age / sex / ethnicity breakdown of all women eligible for the study pseudonymised line-level for those who do not return a sample
- The number of women aged 25-64 years
- Cervical screening coverage (age-appropriate and 5 year)
- The number of women who are eligible over the study period (i.e. aged 25-64 with a
  cervix who are (i) at least 6 months overdue cervical screening or (ii) women who have
  never been screened or reach the 15- or 27-month anniversary of their last cytology
  due date (both arms).
- The number of eligible women who consulted a GP, nurse or healthcare practitioner at least once during the study period (to calculate the proportion of women invited and response rates) Intervention arm only
- The proportion of eligible women who order an SSK:
  - Online
  - By returning a form
  - Via text message
- Cervical screening data all clinical codes relating to cervical screening (cytology and histology) for all women in the study (GP level randomised and individually randomised) – pseudonymous line-level data for those who do not return a sample.
- Passive follow up of cervical cytology tests and histology results for all women in the study (GP level randomised and individually randomised) - pseudonymised line-level data for those who do not return a sample. This data will be collected from the GP records. Depending on GP practice capacity and resource, they may be asked to ensure they have updated the GP records with data from the NHAIS national screening database prior to final data collection.

Record Retention and Archiving Study data will be stored securely and made available for audit. Upon study completion study records will be kept for 5 years as per agreement with Sponsor

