#### 5. STUDY PROCEDURES

#### 5.1. Pre-randomisation

At study start, baseline information will be collected at each GP practice by the research team using an anonymous search of electronic patient records. This will only include high level aggregate data such as 5-year cervical screening coverage for the previous year (before census date) and the number of eligible women. We will also check to ensure that it is possible to identify the number of women who have reached our census date of 15.0-15.99 months or 27.0-27.99 months past their last test due date.

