#### 5.3. Individual-level randomisation

Eligible women will be identified on a monthly basis using GP records (i.e. date of last cytology test entered will be used to calculate time since last test). This will be carried out by a member of the GP practice admin team using a pre-written search of the electronic GP records. All eligible women in participating GP practices who have never been screened or who reach the 15 month (or 27 month) anniversary of their last test due date and have not been screened (by cytology or self-sample) will be randomised (2:1:1) to receive usual care (Group A), a letter inviting them to order a self-sampling kit (Group B) or a self-sampling kit

(Group C). This will include women who have been offered self-sampling opportunistically in the intervention arm GP practices.

GP practices will randomise eligible women either using a computer-generated list of random numbers that will be provided by the study team or using the in-built randomise function in the EPR. We will use a mailing company (PSL Print Management Ltd) to assemble kits and subsequently distribute letters and kits to women on the GP practices' behalf. This vendor is fully ISO27001 and GDPR compliant. It will be recommended to GPs that they should put a data notice on their website / in the practice stating that patient's data may be submitted to a third-party organisation as part of a cervical screening research study.

A patient information leaflet, a self-sample instruction sheet and an HPV information leaflet will be included with the invitation letters sent to women in Groups B and C.

Women invited to order kits (Group B) will be able to choose from different options for ordering kits. The currently planned options include:

- Ordering kits online (from a secure website)
- Ordering kits by returning a mail order form (using a freepost envelope)
- Ordering kits by text message

The inclusion of ordering kits by text message will depend on each GP practices preferences and existing text message software. There are several different platforms available for text messaging at GP practices, capability/functionality varies, and some practices may not use text messages at all. We envisage that the process will comprise a weekly email of text message replies (auto-generated by the text message platform) that is sent to a member of the GP practice admin team who will then send out kits.

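### The change in practice coverage could include a record-completion artefact: an NHAIS update is foreseen before the final extract but not before the baseline search

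*Protocol*

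**What the plan says.** **Baseline.** Protocol 5.1: "At study start, baseline information will be collected at each GP practice by the research team using an anonymous search of electronic patient records". What is collected is "high level aggregate data such as 5-year cervical screening coverage for the previous year". No updating of the records beforehand is mentioned.

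**Eligibility for individual randomisation.** Protocol 5.3 uses monthly searches of GP records, in which the "date of last cytology test entered will be used to calculate time since last test". Again no update is mentioned.

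**Final extract.** Protocol 9.2: "Depending on GP practice capacity and resource, they may be asked to ensure they have updated the GP records". The same sentence gives the source and the timing: "updated the GP records with data from the NHAIS national screening database prior to final data collection". This is the only update step in the document, and it is conditional.

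**Measures that use both readings, or the final one.** Protocol 8.2 says the team will examine whether it can extract "Change in cervical screening coverage at each practice", to judge the impact of self-sampling on coverage, and "Cervical screening status at the end of the passive follow up period". Section 2.3.3 lists the coverage objective as exploratory.

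**Level of data.** Section 9.2 plans to collect all cervical screening codes for women in the study, at pseudonymised line level for those who return no sample. Sections 5.9 (individually randomised women who return no sample) and 10.5 (controls) allow anonymous aggregate data only.

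**The concern.** A change in coverage can be read as change only if both readings are equally complete. Under the text as it stands, a test done before the study but absent from the GP record is missed by the baseline search. It appears in the final extract if that practice has meanwhile updated from NHAIS. Final minus baseline then rises although nobody has been screened.

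The update depends on administrative capacity, so the artefact would arise at some practices and not at others. With about six practices per arm, chance alone could leave the two arms unequally updated. Differences in coverage change between practices or arms would then partly reflect record keeping. The aim of the study refers to increasing coverage, so this exploratory figure is likely to be quoted.

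**Working it through.** The protocol gives no expected change in coverage, so there is no figure to reproduce. The following gives scale only.

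**Inputs from the protocol**
- Overdue women in 13 practices: 8420 (8.1).
- Coverage in the CCG: 64.4%, age-appropriate, 2015/16 (3.2).
- Expected opportunistic returns: about 210 (8.1.1).
- Expected returns from postal invitations: 7% of 1250 and 12% of 1250 (8.1.2).

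**Assumption**
- f, the share of apparently overdue women with a test inside the coverage window that NHAIS holds and the GP record lacks. The protocol gives no value. I take 1% to 3% and show higher values for reference.

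**Step 1: women behind the coverage figure.** If the uncovered 35.6% corresponds to the 8420 women, the total is 8420 / (1 − 0.644) = 23,652 women aged 25-64.

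**Step 2: benchmark.** Expected self-samples are 210 + 0.07 × 1250 + 0.12 × 1250 = 210 + 87.5 + 150 = 447.5. As coverage, 447.5 / 23,652 = 1.89 points if every sample counted as screening. The synopsis range of 175 to 300 postal returns gives 385 to 510 samples, or 1.63 to 2.16 points. By section 5.10 a self-sample does not change national screening status, so the contribution of the samples to recorded coverage may be smaller.

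**Step 3: artefact at an updated practice.** Apparent rise = f × (1 − 0.644).

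| f | Women reclassified if all practices update (f × 8420) | Apparent rise, points | Ratio to 447.5 samples |
|---|---|---|---|
| 1% | 84 | 0.36 | 0.19 |
| 2% | 168 | 0.71 | 0.38 |
| 3% | 253 | 1.07 | 0.56 |
| 5% | 421 | 1.78 | 0.94 |
| 10% | 842 | 3.56 | 1.88 |

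The ratio does not depend on the 64.4%. The artefact equals the benchmark when f = 447.5 / 8420 = 5.3%.

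**Step 4: difference between practice arms.** Artefact difference = f × 0.356 × (share updated in one arm − share updated in the other).
- All practices update, with equal f: 0.
- 4 of 6 against 2 of 6, f = 1% to 3%: 0.12 to 0.36 points (0.59 at f = 5%).
- One arm only, f = 1% to 3%: 0.36 to 1.07 points.

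**Step 5: Groups A, B and C, if end status is counted without test dates.** Apparent proportion screened = f + (1 − f)p, so a difference between groups shrinks by the factor (1 − f). With assumed true values of 5%, 10% and 15% and f = 3%, the groups show 7.85%, 12.7% and 17.55%. The difference C − A moves from 10.0 to 9.7 points (9.5 at f = 5%).

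**Step 6: after the fix.** If both readings come from the same final records by test date, a back-filled older test enters both and adds 0 points to the change. Under a test-date rule it adds 0 to follow-up screening.

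**The case against.** Much can be said on the other side.

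- **The update may not happen.** Practices may be asked, and only if they have capacity. The protocol is silent on a baseline update; it does not exclude one. This stands: the artefact is possible, not certain.
- **The measure is peripheral.** Coverage impact is exploratory, and 8.2 asks only whether the data can be extracted. Uptake numerators come from the laboratory (Appendix 1) and are untouched. This stands and limits the weight of the point.
- **Date rules belong in the SAP.** This stands in part. A derivation rule can be left to the SAP, but the unequal completeness comes from the protocol's own collection steps. An aggregate reading taken without a date rule cannot be repaired afterwards.

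Two stronger readings are tempting. A reader might infer that back-filled tests will pass for screening after randomisation and distort the comparison of Groups A, B and C. The documents do not support that. A back-filled test normally carries its own date, so with the line-level codes of 9.2 it would show that the woman was not overdue when randomised. Only undated or aggregate status, as 5.9 and 10.5 would imply for some women, lets it mislead. Randomisation within practice then makes the error balanced in expectation.

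A reader might also infer that the artefact is 0.5 to 1.6 times the whole expected effect. That requires 1% to 3% of all women aged 25-64 to change status (about 237 to 710 women, or 2.8% to 8.4% of the overdue). Applied to the overdue women, in whom a missing test can matter, the same percentages give about 0.2 to 0.6.

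**Conclusion.** The point holds in a limited form. Followed as written, the protocol allows the practice-level coverage change to be the difference of two readings of unequal completeness, with the inequality confined to practices that updated.

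Under the assumed 1% to 3% of overdue women, the artefact is about 0.4 to 1.1 coverage points, against a benchmark of about 1.9. This rests on an assumed f, on the missing tests falling inside the coverage window, and on equating the CCG-wide uncovered share with the 8420 women. The 64.4% is age-appropriate coverage, whereas 5.1 names 5-year coverage, whose uncovered share may differ. The points are therefore approximate.

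The three-group comparison faces only raised levels and slight dilution, and only without dates. The primary uptake numerators are not affected. The change is worth making because it is cheap and must be in place before the extract.

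**What to change.** In Protocol 8.2 and 9.2:

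1. At the final extract, run the same aggregate coverage search at each practice with two reference dates, study start and end of follow-up. Take the change from these two readings, and report it beside the baseline reading collected at study start.
2. Count a test as follow-up screening only if its test date falls after study start, or after randomisation for Groups A, B and C, whenever it was entered. Apply the rule to aggregate counts as well as line-level data.
3. Record which practices updated from NHAIS, and show the coverage change separately for updated and non-updated practices.
4. Reconcile 5.9 and 10.5 with 9.2 on whether women who return no sample and controls contribute aggregate or line-level data, since this decides how rule 2 is applied.

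**Cost.** More than analysis wording, but small. The dated codes in 9.2 cover women in the study, while coverage needs all women aged 25-64, so each practice must run one additional back-dated aggregate search. Women who left a practice before the final extract are lost from the rebuilt baseline, which is why both baselines should be shown.

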#### 10. ETHICS

#### 10.1. Ethics approval

Ethics approval for the study will be obtained from the London - Brighton & Sussex Research Ethics Committee (REC) ref 17/LO/1655).

#### 10.2. Informed consent procedures

The patient information sheet and an information leaflet on HPV will be provided to all women who receive self-sampling kits and all those invited to order kits. As only women who wish to participate will return a self-sample (i.e. opt-in), consent is implicit.

#### 10.3. Opportunistic offering of self-sampling

GP primary care is a busy and time-pressured environment with an average GP consultation length of just 9 minutes.[22] In a previous study of opportunistic offering of self-sampling in GP primary care the consent procedure consisted of a brief (2 min) study explanation and verbal consent. This simplified approach was suggested by the reviewing REC committee (Brighton and Sussex NRES Committee 13/LO/1441) and worked well for the study with no issues raised. Therefore, we intend to use the same verbal consent procedure for this study. Consent to accept a self-sampling kit will be recorded in the women's GP medical record.

#### 10.4. Women randomised to receive or order an SSK in the post

Consent will be implicit by return of a self-sample.

SSKs will come with a form which will contain the women's details (to identify the women) and statements detailing precisely what the study involves and what they are agreeing to by returning a self-sample (e.g. regarding permission for the study team to access to medical record data). The form will state clearly what the women are consenting to by returning their sample.

Women who order a SSK online (will only apply to women randomised to Group B who are invited to order a SSK) will be asked to provide explicit consent to storing their personal data (encrypted) on a secure database at QMUL and for this data to be shared with trusted third parties for the purposes of assembling, sending and analysing the kit/sample. This will be in the format of an online pop up window during the SSK ordering process, and their data will only be saved once they click "I agree". Personal data collected on the website will be stored but not accessed by QMUL, as the PID collected will only be used for SSK order fulfilment (carried out by PSL Print Management Ltd).

#### 10.5. Women randomised to usual care (control group)

Women who are randomised to usual care (control group) will not provide consent for the study. Only anonymous aggregate data will be collected for these women.

#### 11. SAFETY CONSIDERATIONS

We do not anticipate any major safety concerns for the study. Vaginal self-sampling using flocked swabs has been safely performed in several studies.[17, 23-26]

#### 12. SAFETY REPORTING

#### 12.1. Annual Safety Reporting

This is a low risk study and we do not anticipate any safety issues.

As per standard practice, the CI will send the Annual Progress Report to the main REC using the NRES template (the anniversary date is the date on the MREC "favourable opinion" letter from the MREC) and to the sponsor.

#### 13. MONITORING & AUDITING

A member of the research team will audit and monitor study procedures as agreed in the study monitoring plan (e.g. recruitment, recording of consent, and anonymous data downloads to check data quality).

The study may be audited internally by KCL.

#### 14. USER INVOLVEMENT

User representatives will be involved in the study design and review of trial results. We have already sought user feedback for all the study documentation that participants will receive, and this has been incorporated. As the study will be held in GP primary care, we have involved GPs in helping us develop the study processes

#### 15. FINANCE AND FUNDING

The pilot study will be funded by a programme grant awarded by Cancer Research UK to [name].

#### 16. INDEMNITY

The study was initially sponsored by Queen Mary University of London and suitable indemnity was in place during this time. Relocation of the study team to King's College London in January

2018 resulted in the change of sponsorship from Queen Mary University of London to King's College London. King's College London is currently sponsoring the study and has arranged for suitable indemnity to be in place.

#### 17. DISSEMINATION OF RESEARCH FINDINGS

We plan to disseminate the findings of our research via conference presentations and publication in peer-reviewed journals.

### APPENDIX 1 – TABLE OF OBJECTIVES, ENDPOINTS & ASSESSMENT METHOD

Primary Objective	Endpoints	Assessment Method
To estimate the proportion of	Uptake of self-sampling	Opportunistic: number of eligible women with self-sample returned (using
women who provide a self-sample	within 6 months after	data provided by lab) as a % of total eligible women with Read codes for kits
when:	invitation	offered as per GP records
Offered kits opportunistically		vs
Sent a kit directly (opt-out)		Sent a kit directly (opt-out): number of women returned self-sample (using
Invited to order a kit (opt-in)		data provided by lab) as a % of total eligible sent kit directly
		vs
		Invited to order a kit (opt-in): number of women returned self-sample (using
		data provided by lab) as a % of total eligible sent letter (and separately for each
		method of kit ordering as a % of total eligible sent letter)
Secondary Objectives	Endpoints	Assessment Method
To estimate the proportion of	Attendance at follow up	Number of eligible women who test HPV positive on a self-sample and (i) have
women who test HPV positive on	(cytology or colposcopy)	codes for cytology or colposcopy attendance in their GP records within 6
a self-sample and attend for follow	amongst eligible women	months of HPV positive result and (ii) who have CIN2+ recorded in their GP
up within 6 months of a positive	within 6 months of testing	records; as a % of all eligible women who test HPV positive on a self-sample
result	HPV positive on a self-	

	sample and histological confirmation of CIN2+	
To assess the logistics of testing samples, recording results and giving women their results in a timely manner.	testing and results	
Exploratory Objectives	propurage GPs to offer self-s	campling opportunistically to women who are overdue cervical screening consult

To pilot a variety of approaches to encourage GPs to offer self-sampling opportunistically to women who are overdue cervical screening consult for any reason. Where GP functionality exists text message ordering will also be utilised, but it is unclear how many GP sites will have the functionality to offer this. Availability of additional services will be recorded to see if this is a viable method to take forward into future work

To pilot a variety of approaches to facilitating women who wish to order a self-sampling kit

To compare demographic and cervical screening status (never screened, overdue, up-to-date) between responders and non-responders

To examine the consultation rates and response rates (numbers offered, accepted, declined and returned as a proportion of total number of eligible women, reasons for declining kits, kit offers by health professional type) for eligible women in the opportunistic (intervention) arm.

To assess the impact of offering self-sampling on cervical coverage using passive follow up data

To carry out analysis on residual samples that could help inform management for cervical screening in the future

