#### **STUDY SYNOPSIS**

Chart Title	A Landan LIDV Call Compline Dilat			
Short Title	A London HPV Self Sampling Pilot			
	A pragmatic, factorial cluster randomised controlled pilot study (a 2 x3 factorial design, with the 3-way (individual level) randomisation nested within the 2-way (GP-level) randomisation.			
Methodology	GP practices will be randomised 1:1 to either offering self- sampling kits (SSK) opportunistically to women overdue (>6 months) cervical screening when they present for any reason (intervention arm) or usual care (control arm).			
	The second (nested) randomisation will be individual level randomisation of women within each GP practice who have never been screened or who reach the 15- or 27-month anniversary of the date their last cytology test was due without being screened (by self-sample or cytology). 2:1:1 to either: Group A Usual care (control). Group B Receiving a letter inviting them to order a kit, or Group C: Receiving a kit in the post.			
Research Sites	~13 GP practices in London			
Aim	To assess feasibility and optimal approaches for offering self-sampling to cervical screening non-attenders in London to increase coverage.			
Objectives	A summary table of study objectives, endpoints and method of assessment is located in Appendix 1 .			
	For GP-level randomisation:  ~8420 women in total will be eligible (i.e. >6m overdue cervical screening) within 13 GP practices of which we estimate the following:  • ~500 will be offered SSKs opportunistically (330 will accept and ~210 will return a self-sample)			
Number of participants	For individual-level randomisation:  • ~5000 (i.e. never screened or 15- or 27-month anniversary of the date their last cytology test) will be individually randomised  • ~2500 will receive an SSK or letter inviting them to order an SSK via individual level randomisation of which 175-300 will return a self-sample			
Inclusion criteria	
 
GP-level randomisation
 
Women aged 25-64 years who are eligible for cervical screening and are least 6 months overdue (i.e. no cervical cytology recorded in the GP records in the past 3.5 years if aged 25-49 or 5.5 years if aged 50-64)
 
			

·	
	Individual-level randomisation
	Never-screened women & women who reach the     15 months* of last smear due date (and not screened by smear or self-sample)      Women unable to provide informed consent (e.g.
	because of learning difficulties)

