## KING'S College LONDON

#### STUDY PROTOCOL

#### 5.2. Cluster randomisation

#### 5.2.1. Intervention arm - Opportunistic offering of self-sampling

GP practices randomised to the intervention arm will have an alert set up on their electronic patient record (EPR) software to automatically flag potentially eligible women when their record is loaded. Specifically, EPR systems will be programmed to flag women aged 25-64 who are at least 6 months overdue cervical screening (i.e. no cervical cytology recorded in the past 3.5 years (if aged 25-49) or 5.5 years (if aged 50-64) and no codes for hysterectomy or amputation of cervix).

Doctors, nurses and healthcare assistants (HCA)/assistant practitioners (AP) will be asked to offer self-sampling kits to women who have been flagged when they consult for any reason. In practice, this will be done on a case-by-case basis at the discretion of the healthcare professional consulted (e.g. SSKs will not be offered to women who are terminally ill). The study invitation will comprise a brief conversation (~2 minutes) at the end of the consultation. Once eligibility has been confirmed, women who agree will be given a self-sampling kit.

A study template will be set up in the GP electronic patient record system. When eligible women are offered kits, the consulting health professional will use the template to record:

- 1) Whether or not the study kit was accepted.
- Study kit number (if accepted).
- Reason for declining (if applicable)

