#### 8.1.1. Intervention arm – Opportunistic offering of self-sampling

With six GP practices randomised to the intervention arm, there would be some 4000 eligible women. Based on a previous study[19]) we estimate that 60% will consult their GP practice over one year, 500 (21%) will be opportunistically offered a self-sampling kit and  $\sim$ 330 (14%) will accept (4000\*0.60\*0.14). An estimated 210 (9%) (4000\*0.6\*0.09) would return a self-sample for HPV testing. Therefore, the proportion of women >6m overdue cervical screening who will return a sample when opportunistically offered a kit (i.e.  $\approx$ 210/2400) could be estimated with a 95% confidence interval of width  $\pm$ 1.0%.

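### The ±1.0% precision given for opportunistic uptake is calculated per woman who consults, but the primary endpoint is defined per woman offered a kit, where it is about ±4.3 points

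*Protocol*

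**What the plan says.** **Endpoint.** Section 2.3.1 asks what proportion of women provide a self-sample when offered a kit opportunistically, sent a kit, or invited to order one. Appendix 1 makes this operational. For the opportunistic mode it takes returned samples from "data provided by lab) as a % of total eligible women with Read codes for kits" offered. For the other two modes the denominator is the eligible women sent a kit or sent a letter.

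**Precision.** Section 8.1.1 starts from six intervention practices, in which "there would be some 4000 eligible women". It then assumes that "60% will consult their GP practice over one year, 500 (21%) will be opportunistically offered a self-sampling kit", that 14% accept and that 9% (about 210) return a sample. It concludes that the proportion of overdue women "who will return a sample when opportunistically offered a kit" is about 210/2400 and can be estimated to within ±1.0% with 95% confidence. The synopsis repeats the lower end of this sequence: about 500 "will be offered SSKs opportunistically (330 will accept and ~210 will return a self-sample".

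**Other bases.** Section 8.2, under the opportunistic arm, plans a further set of measures: "Using electronic GP record searches: The proportion of eligible women who" consult, are offered a kit, accept it and return an adequate sample. An exploratory objective in section 2.3.3 also uses all eligible women as its base.

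**How offers arise.** Section 5.2.1 says of the offer that "this will be done on a case-by-case basis at the discretion of the healthcare professional consulted".

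**The concern.** The words in section 8.1.1 describe return given an offer, while the number beside them is return given a consultation. These quantities differ almost fivefold in expected value (42% against 8.75%). A reader would take ±1.0% as the precision for the opportunistic part of the primary objective, when it belongs to another proportion.

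Estimating this proportion is one of the pilot's primary objectives, so the precision statement is the main justification for the size of the opportunistic arm. The label also invites a reader to set 9% beside the 12% and 7% assumed in section 8.1.2. Those two are per woman sent a kit or letter, whereas the 9% is per woman who consults.

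**Working it through.** **Inputs (all from section 8.1.1).** Eligible women in intervention practices 4000; 60% consult; of those, 21% are offered a kit, 14% accept and 9% return a sample. The rounded counts used in the text are 500, 330 and 210.

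**Step 1: the base of the percentages.**
- Consult: 4000 × 0.60 = 2400
- Offered: 2400 × 0.21 = 504 (text: 500)
- Accept: 2400 × 0.14 = 336 (text: about 330)
- Return: 2400 × 0.09 = 216 (text: 210)

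All three percentages are therefore per woman who consults. The Background section agrees: it gives the earlier pilot's 9% as a share of non-attenders who consulted.

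**Step 2: reproduce the plan's figure.** The 95% half-width is 1.96 × √[p(1 − p)/n].
- p = 210/2400 = 0.0875
- 1.96 × √(0.0875 × 0.9125/2400) = 1.96 × 0.00577 = 0.0113, or ±1.1 points

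The unrounded count of 216 gives ±1.14. The Wilson interval for 210/2400 is 7.7% to 9.9% and the Clopper-Pearson interval 7.6% to 10.0%. The stated ±1.0% is not reproduced to the one decimal shown, and agrees only when rounded to a whole point. This difference is small.

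**Step 3: the endpoint as Appendix 1 defines it.**
- p = 210/500 = 0.42
- 1.96 × √(0.42 × 0.58/500) = 1.96 × 0.0221 = 0.0433, or ±4.3 points

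The Wilson interval is 37.8% to 46.4% and the Clopper-Pearson interval 37.6% to 46.5%. With unrounded counts, 216/504 = 42.9%, again ±4.3 points. The half-width is 4.33/1.13 = 3.8 times that of 210/2400.

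**Step 4: the three bases together, before clustering.**

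| Base | Proportion | 95% half-width |
|---|---|---|
| Offered (primary objective, Appendix 1) | 210/500 = 42.0% | ±4.3 points |
| Consulting (number used in 8.1.1) | 210/2400 = 8.75% | ±1.1 points |
| Eligible (8.2 and 2.3.3) | 210/4000 = 5.25% | ±0.7 points |

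**Step 5: clustering.** The protocol gives no intracluster correlation, so a range of 0.01 to 0.05 is assumed here for illustration. With six equal practices the design effect is 1 + (n/6 − 1) × ICC.
- n = 500: design effect 1.82 to 5.12, half-width ±5.8 to ±9.8 points
- n = 2400: design effect 4.99 to 20.95, half-width ±2.5 to ±5.2 points

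The figures in Step 4 are thus the most favourable values.

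**The case against.** The case for leaving the text alone has several parts. This is a feasibility pilot, and section 8.2 says that it has no formal primary outcome measure. Section 8.1.1 shows its ratio openly, and the Background describes the same 9% correctly. No recruitment target, randomisation or decision rule is shown to depend on the ±1.0%. These points limit the seriousness. They do not remove the error, because sections 2.3.1 and 2.4 and Appendix 1 still name a primary objective and endpoint, and the only precision offered for its opportunistic part is for another quantity.

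A reader might infer more than the documents support:

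- **That the three modes cannot be compared.** Appendix 1 follows the primary objective and gives each mode a per-invitation denominator: offered, sent a kit, or sent a letter. The text out of line is in section 8.1.1.
- **That Appendix 1 favours opportunistic offering and needs an all-eligible denominator.** Return per offer is a legitimate measure with a stated rationale: in the earlier study offering varied widely between practices (11% to 36%) while return among women offered was constant. The per-eligible proportions are already planned. Dividing by 4000 would still not give a like-for-like contrast. The opportunistic base is all women at least six months overdue in intervention practices. Groups B and C are never-screened women and those at the 15- or 27-month anniversary, in all practices.
- **That the denominator reverses the ranking.** Setting 42% or 5.25% against 12% and 7% mixes planning assumptions for different populations, so it does not predict the result.
- **That offers will be under-recorded.** No section documents this. The template in section 5.2.1 records acceptance and kit number. Limiting the numerator to coded offers is a safeguard and does not answer a known fault.

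One part of the comparability worry stands. Offers reach only women who consult and are made at the professional's discretion. Return per offer therefore says nothing about reach, and the contrast with Groups B and C is not randomised.

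**Conclusion.** The point holds as an error of label and precision in section 8.1.1. The ±1.0% belongs, approximately, to the proportion of consulting women who return a sample; its value is ±1.1 points around 8.75%. For the primary endpoint as defined, the expected precision is ±4.3 points around 42%, about 3.8 times wider. This rests on the protocol's own counts of 210, 500 and 2400 and on independent observations. Allowing for six practices would widen both intervals by an amount the protocol gives no means of fixing. The endpoint definition in Appendix 1 is sound and consistent with the primary objective.

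**What to change.** **Section 8.1.1.** Describe 210/2400 as the proportion of women who consult, with ±1.1%. Add the precision of the primary endpoint: 210/500 = 42%, ±4.3 points. Say that both are before allowance for clustering by practice.

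**Appendix 1.** Keep the per-offer denominator. State that the opportunistic numerator counts only women with a coded offer. Report the per-consulting and per-eligible proportions beside it. Note that any contrast between opportunistic offering and Groups B or C is descriptive and non-randomised, and that return per offer does not measure reach.

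**Cost.** Wording only. The counts needed are already planned in sections 8.2 and 9.2, and neither the design nor the sample size changes. The downside is that the stated precision becomes less favourable.
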